Objective	Brief Description/ Justification of Outcome Measure	Outcome Measured By	Time Frame

Assess the effectiveness of NRTS compared to ET on smoking heaviness
	
In addition to assessing the effectiveness of NRTS on abstinence, we want to assess the effect of NRTS on cessation-related behavior including reducing heaviness of smoking.
	
Smoking heaviness indicates cigarettes per day. Timeline follow-back measure of cigarettes per day on each of the past 7 days at 6-months post quit. We will measure cigarettes per day at baseline. We will then compute cigarettes per day at each follow-up timepoint by summing the number of cigarettes each person reports on each day of their follow-up survey and dividing by 7.
	
6 months following baseline.

Assess whether cessation medication utilization mediates the effectiveness of NRTS on 6-month abstinence.
	
Treatment utilization is one mechanism by which NRTS is hypothesized to have its effect.
	
Self-report survey items of use of the nicotine patch and nicotine lozenge at 1-, 3-, and 6- months post baseline. These items will be dichotomized as used NRT vs. hasn't used NRT in the 6 months post intervention. In addition, days of NRT use will be computed.
	
6-months following baseline.

Objective	Brief Description/ Justification of Outcome Measure	Outcome Measured By	Time Frame

Assess whether attitudes towards NRT (safety and efficacy) mediate the effectiveness of NRTS on 6-month abstinence.
	
We hypothesize that one mechanism of action of NRTS is to cause more favorable attitudes towards NRT.
	
Self-report survey items at baseline, 1-month, 3-month and 6-month surveys of perceptions of nicotine replacement therapy safety and efficacy. We will assess perceptions of NRT efficacy on a 5-point Likert-scale where higher scores indicate greater efficacy. We will assess safety with a single item measure on a 5-point Likert scale where higher scores indicate greater perceptions of NRT safety.
	
6-months following baseline.

Objective	Brief Description/ Justification of Outcome Measure	Outcome Measured By	Time Frame

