12.1 Study Hypotheses

Hypothesis 1 (primary): Participants receiving the NRTS intervention will have a higher frequency of biochemically confirmed abstinence at 6 months post enrollment compared to ET.

Hypothesis 2a: Participants receiving NRTS will be more likely to have a 24-hour quit attempt than ET.

Hypothesis 2b: Participants receiving NRTS will have greater reductions in smoking heaviness compared to baseline than ET.

Hypothesis 3a: Use of nicotine replacement therapy (patch and lozenge) will mediate the effect of NRTS on biochemically confirmed abstinence at 6 months post enrollment.

Hypothesis 3b: Perceptions of NRT safety and efficacy will mediate the effect of NRTS on biochemically confirmed abstinence at 6 months post enrollment.

Hypothesis 3c: Intention to use NRT will mediate the effect of NRTS on biochemically confirmed abstinence at 6 months post enrollment.

Hypothesis 3d: Intention to quit smoking will mediate the effect of NRTS on biochemically confirmed abstinence at 6 months post enrollment.

Hypothesis 4a: NRTS will be considered feasible to administer in dental settings.

Hypothesis 4b: NRTS will be acceptable to practitioners and patients.

Hypothesis 5: NRTS will be cost effective.

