12.3 Final Analysis Plan

Demographics, baseline smoking history, and smoking behavior will be summarized across the aggregate sample and descriptively compared between clinics and treatment groups. Any large imbalances at the individual level will be considered for inclusion as a covariate. We will include the cluster-level stratification factors as covariates (minority race/ethnicity and payer mix). The distribution of each of the primary and secondary

study outcomes will be assessed using both parametric and graphical methods to determine the most appropriate modeling distribution (e.g., binomial, normal and zero-inflated distributions). Transformations of the outcome (e.g., log transform towards normality) will be considered if a model does not meet its assumptions. We will report point estimates (unstandardized effects size/magnitude) and associated 95% confidence intervals (precision). All hypotheses will be evaluated at a two-tailed alpha level of .05.

Sex and race as biological variables. We will test for effect modification by sex and race for the primary outcome. However, insofar as our proposal does not include hypotheses regarding sex and racial differences in treatment outcomes, we will conduct our hypothesis testing using both sexes and all races combined. This will be accomplished by adding a product term of group and sex or race (each will be evaluated separately) to the model. Given the low power for interaction effects, we will report the simple effects and associated confidence intervals both numerically and graphically to determine the nature of any effect modification.

[figure not shown]

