To test hypothesis 1, we will compare treatment groups with respect to the primary outcome (biologically verified 7-day PPA from use of combusted tobacco at six months) using generalized hierarchical linear modeling⁴³⁻⁴⁵ with a binomial distribution and logit link (aka mixed effects logistic regression) that account for the clustering of individual observations within dental practice, while adjusting for various patient and practice related factors.^{46,47} The first level of the model (participant) will include any individual level covariates. The second level of the model will include the fixed effects for treatment group (ET=0, NRTS=1) and the cluster level stratification factors and a random effect for the participant level intercept. A significant coefficient for the treatment group indicator with an odds ratio > 1 would provide support for the effectiveness of NRTS on smoking abstinence at 6 months.

This same model framework will be used to examine the secondary outcomes of abstinence at 1 month and abstinence at 3 months and whether there was a quit attempt at 1,3, or 6 months. To determine whether the intervention had an effect on smoking heaviness over time, we will use a three-level hierarchical linear model that will account for the nesting of observations within persons and persons nested within practices. The first level of the model will include a categorical fixed effect for time (baseline [reference group], 1 month, 3 month, 6 month). The second level of the model will include fixed effect for any individual level covariates and random coefficient for the level 1 intercept. The third level will include for treatment group and the cluster level stratification factors and a random effect for the participant level intercept, including the terms for the time vectors representing the cross-level interactions. Significant terms for the cross-level interaction would indicate that the change in smoking heaviness differed

by treatment group, and will be followed up with examination and plots of the estimated marginal means do determine whether those in the NRTS group had greater decreases in smoking heaviness compared to the ET group.

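### The smoking-heaviness model has random intercepts only and no single deciding test, so the 5% level for hypothesis 2b is not assured

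*Protocol*

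**What the plan says.** Protocol section 12.1 states hypothesis 2b as a comparison of change: "Participants receiving NRTS will have greater reductions in smoking heaviness compared to baseline than ET".

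Section 12.3 sets out the model level by level. It is a "three-level hierarchical linear model that will account for the nesting of observations within persons and persons nested within practices".
- Level 1 has a "categorical fixed effect for time (baseline [reference group], 1 month, 3 month, 6 month"), so there are three treatment-by-time terms.
- Level 2, the person, has a "random coefficient for the level 1 intercept".
- Level 3, the practice, has treatment arm, the stratification factors and "a random effect for the participant level intercept, including the terms for the time vectors representing the cross-level interactions". No random time effect is written at either level.

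The decision rule is "Significant terms for the cross-level interaction would indicate that the change in smoking heaviness differed" by treatment group, followed by inspection and plots of marginal means. No joint test, single time point or adjustment for multiple terms is named. The same section says "All hypotheses will be evaluated at a two-tailed alpha level of .05". The outcome table in section 4.2 gives a 6-month time frame and describes the measure as "Timeline follow-back measure of cigarettes per day on each of the past 7 days at 6-months post quit".

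**The concern.** The treatment effect in this model is a difference between arms in change from baseline. A random intercept shifts all of a person's or practice's measurements by the same amount, so it drops out of that change. If practices differ in how far their patients cut down, that variation is not in the standard error of the tested terms, although practice is the unit of randomisation. The confidence intervals would then be too narrow.

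Separately, three terms are available and the rule does not say whether one of them, any of them or all of them jointly must be significant. At stake is whether a positive finding on this secondary outcome carries the stated 5% error rate.

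**Working it through.** **Inputs from the protocol.** 50 practices of 24 patients, hence 25 practices and 600 patients per arm (sections 5 and 12.2). ICC 0.013, range 0.010 to 0.016, stated for CO-verified abstinence only (12.2). Two-sided 5% (12.3). Four time points, hence three interaction terms (12.3).

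**Assumption.** The protocol gives no between-practice variance for change in cigarettes per day. Let ρ be the share of within-person variance that is practice-by-time variance; this equals the ICC of change. The abstinence range is borrowed for ρ, with ρ = 0 shown beside it.

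**Step 1: reproduce the plan's own figure.** Section 12.2 gives no figure for heaviness, so the reference is the Table 11.1 cell with ET rate 5.5%, difference 5.0 points and ICC 0.013.
- Effective n per arm = 600 / (1 + 23 × 0.013) = 600 / 1.299 = 461.9.
- SE = √[(0.055 × 0.945 + 0.105 × 0.895) / 461.9] = 0.01778.
- Power = Φ(0.05 / 0.01778 − 1.96) = Φ(0.853) = 80.3%, as printed.

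All 45 cells reproduce within 0.3 points. The protocol's own sample-size calculation therefore uses the design effect 1 + 23 × ICC.

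**Step 2: what the model uses and what is true.** With balanced data and residual variance σ², both intercepts cancel. The model variance of each interaction term is 2σ²(1/600 + 1/600). The three terms correlate 0.5 through the shared baseline. With practice-by-time variance, the true variance is larger by the factor 1 + 23ρ.

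**Step 3: false-positive rates of the model as written.**
- One term: 2[1 − Φ(1.96 / √(1 + 23ρ))].
- Joint 3-df test: P(χ²₃ > 7.815 / (1 + 23ρ)).
- Any of three: from the trivariate normal with correlation 0.5.

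| ρ | 1 + 23ρ | One term | Joint 3-df | Any of three |
|---|---|---|---|---|
| 0 | 1.000 | 5.0% | 5.0% | 12.5% |
| 0.005 | 1.115 | 6.3% | 7.2% | 15.6% |
| 0.010 | 1.230 | 7.7% | 9.6% | 18.7% |
| 0.013 | 1.299 | 8.6% | 11.1% | 20.5% |
| 0.016 | 1.368 | 9.4% | 12.7% | 22.3% |

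**Step 4: checks.**
- Simulation at ρ = 0.013 (6000 trials) gave 8.8%, 11.3% and 21.3%.
- Three-level models fitted to 500 simulated trials at ρ = 0.013 gave 49/500 = 9.8% for the 6-month term and 102/500 = 20.4% for any term.
- If the practice deviation is instead one shift common to all follow-ups, ρ = 0.013 gives 9.1%, 8.4% and 19.8%. The joint figure therefore depends on the pattern of variation as well as its size.

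**Step 5: after repair.** A test on practice-mean change with 48 df, for ρ from 0 to 0.05, gave 4.4% to 5.5% for the 6-month term and 4.4% to 5.6% for the joint test. With clustering repaired but any of three terms still counting, the rate stayed at about 10% to 13%. Both parts need attention.

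**The case against.** A reader might infer that the error rate of this analysis is simply well above 5%, or that the test ignores clustering altogether. The documents support neither.

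- **The size is not fixed by the protocol.** The ICC of 0.013 belongs to a binary abstinence outcome at one time point, and section 12.2 limits its calculations to that outcome. If practices do not differ in change, a single term or a joint test holds 5%. This stands, and every figure above ρ = 0 is conditional. A non-zero value is still plausible. Everyone enrolled smokes at baseline (section 6.1), so abstinence at 6 months is itself a change from baseline, and the protocol expects practices to differ on it.
- **Significant terms may mean a joint test.** Terms of one interaction, followed by probing of marginal means, can be read as an omnibus test with follow-up. The any-of-three rates therefore rest on a reading the text permits but does not state. A joint test removes the multiplicity but not the missing variance component.
- **Clustering is partly modelled.** Practices do have a random intercept. The gap is narrower: practice-by-time variation is not written in. The level-3 sentence is also garbled and could loosely be taken to allow it, though fixed interactions are the plainer reading.
- **A statistical analysis plan, not available here, could settle covariance and contrasts.** That is fair for detail the protocol leaves open, and section 12.3 does leave the outcome distribution open. The random effects, however, are written out level by level, so this is a stated choice.
- **The 6-month time point is not the only candidate.** Section 4.2 also computes cigarettes per day at each follow-up, and 12.3 aims at heaviness over time. This stands; a joint test would serve equally well.

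**Conclusion.** The point holds in conditional form. As specified, the arm-by-time terms for hypothesis 2b carry no between-practice variation in change, and no one test is named to decide, so the stated 5% is not assured. If the ICC of change lies between 0.010 and 0.016, the rate is about 8% to 9% for one term and 10% to 13% for a joint test when practice deviations are independent across visits; with zero practice-level variation both are 5%. If any significant term suffices, it is about 12.5% at zero and 19% to 22% over that range.

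These figures assume balanced data, a Gaussian outcome and a borrowed ICC. The outcome is secondary and the primary analysis is unaffected. The remedy is cheap enough that the change should be made.

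**What to change.** In section 12.3, or in the statistical analysis plan with 12.3 aligned to it:

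1. Add a practice-by-time random effect to the heaviness model. Use a within-person covariance less restrictive than a random intercept, and small-sample degrees of freedom (Satterthwaite or Kenward-Roger) suited to 50 practices.
2. Name one deciding test for 2b: either the arm-by-6-month contrast, which matches the time frame in section 4.2, or the joint 3-df interaction test. Treat the remaining time-point results as supportive.
3. Rewrite the level-3 sentence so that fixed and random terms are listed separately.

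Keep the maximum-likelihood repeated-measures model, which uses the 1- and 3-month data of participants missing at 6 months. A 6-month analysis adjusted for baseline cigarettes per day with a practice random intercept is an alternative, not an equivalent: it conditions on baseline and does not use those earlier data.

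The cost is wording and wider confidence intervals: √1.230 = 1.109 to √1.368 = 1.170, or about 11% to 17% wider at an ICC of change of 0.010 to 0.016. No new data are needed.

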6.2 Participant Exclusion Criteria

A patient who meets any of the following criteria will be excluded from participation in this study:

- Does not own a smart phone with internet access
- Unwilling or unable to provide informed consent
- Myocardial infarction or stroke in the past 3 months
- Pregnant or breastfeeding
- Use of tobacco cessation medication in the past week
- Previously enrolled in the study

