7 STUDY INTERVENTION

7.1 Study Product Description

Nicotine replacement therapy samples will include a 14-day supply of 14mg transdermal nicotine patches and a 14-day supply of 4mg nicotine lozenges.

Electric toothbrushes will be Sonicare brand. The toothbrushes will have the Seal of Approval from the American Dental Association.

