7.4 Study Behavioral Intervention Description

Practices will be randomly assigned to study condition (NRTS or ET). Practices will be instructed not to disclose the intervention condition to the patient participant until after the baseline survey has been completed.

AAR (both conditions): Practitioners (NRTS and ET) will be encouraged to deliver AAR to all patients regardless of trial participation.

Patient participants will receive:

- monogrammed study bag
- study trinkets such as pens and post-it notes
- a brochure published by the ADA describing the effects of tobacco use on oral and general health
- contact information for their state tobacco quitline
- information about tobacco cessation medications
- study contact information
- the follow-up schedule
- condition specific information about NRT/ET
- consent form
- HIPAA form

NRT sampling (NRTS): Practices assigned to NRTS will dispense NRT samples in addition to AAR.

Patient participants will receive: a “starter pack” consisting of a 2-week supply of both nicotine patches (14 mg) and lozenges (4 mg; combination NRT [C-NRT]). Practitioners will spend 1-3 minutes on instruction prior to dispensing samples. Instructions for NRT use are provided on each medication package. We will also include FAQs and information dispelling misconceptions. Practitioners will neither explicitly advise nor discourage combined use or concomitant use with cigarettes. Patients will receive oral and written instructions including how to obtain more nicotine replacement therapy if interested (e.g., from their primary care provider, or purchased over the counter). Practitioners will instruct patients that the samples are an opportunity for smokers to learn about two NRT products that can be used individually or together (participant choice, including none at all). Some suggested uses could be:

- to get experience with the products and determine if they like them
- to reduce smoking or restrict where they smoke

- to make a practice quit attempt
- to get started on quitting

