8.3 Follow up Visits¹

Data collection timepoint 2, Day 0 (allowable range 0-14)

- Following visit, administer after visit survey via email, text, or phone.

Data collection timepoint 3, Day 30 (allowable range 28-44)

- Administer 1-month follow-up survey via email, text or phone.
 - Assess adverse events via survey.

Data collection timepoint 4, Day 90 (allowable range 83-104)

- Administer 3-month follow-up survey via email, text or phone.
 - Assess adverse events via survey.

Data collection timepoint 6, Day 180 (allowable range 173-210)

- Administer 6-month follow-up survey via email, text or phone.
 - Assess adverse events via survey.

Data collection timepoint 7, Day 180 (allowable range 174-234)

- Participants who are abstinent will take a CO test

Data collection timepoint 8, Day 180 (allowable range 173-240)

¹ Note: Participants may choose to complete the survey out of the timeframe without prompting from study staff.

- 10-12 patient participants in NRTS condition complete an interview about acceptability of NRTS and attitudes about future implementation of NRTS

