We will test whether NRT utilization, perceptions of NRT effectiveness and safety, intent to use NRT, and intent to quit mediate the relationship between study group (ET vs NRTS) and smoking abstinence using a cross-lagged panel model (CLPM) in a structural equation modeling (SEM) framework.^{48,49} In a CLPM, the mediator and outcome at time t is regressed on arm, the mediator at $t-1$ and the outcome at $t-1$. Prior to estimating a final model, we will test for stationarity for the structural paths by comparing whether a model in which the paths are invariant fits significantly worse than one in which the paths are free to vary. We will also include the same set of covariates used in the primary analysis as time invariant covariates We will assess model fit using root mean square error of approximation (RMSEA) and the comparative fit index (CFI). Our criteria for good model fit will include an RMSEA of .08 or below⁵⁰ and a CFI of .95 or above.⁵¹ A significant indirect effect,⁵² based on bootstrapped standard errors,⁵³ would provide evidence for mediation.^{48,54} We will account for the clustering of participants within practices by including a random effect for the intercept terms in each path equation by employing the multilevel form of SEM (2-1-1-1 design).^{55,56} We will conduct separate models for each mediator.

Figure X. Cross lagged panel model for testing mediation. Covariates omitted for clarity.

Missing data. For all participants, we will attempt to gather follow-up information and reasons for dropout regardless of protocol completion and censor at the point of drop out. PBRN studies routinely attempt to collect reasons for dropout.⁵⁷ We anticipate

having about 11% attrition, as was found in previous work. We will compare baseline data between those with and without missing data and examine whether there are variables that are related to missingness. Analysis will use maximum likelihood (ML) approaches to produce estimates of the model parameters. One advantage of a ML approach when compared to other approaches such as multiple imputation, is that it makes use of all available data without requiring imputation of missing values, it is more efficient, and maintains congeniality between the missing data estimation and the analytical model.⁵⁸ ML estimates have been shown to be consistent when missing data is related only to covariates and observed values of the outcome.^{59,60}

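### For Hypothesis 3a, the lagged-only mediation model counts quits caused by first-month NRT use as direct, so the indirect effect is understated by the share of the effect that arises before the first follow-up

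*Protocol*

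**What the plan says.** Hypothesis 3a in section 12.1 reads: "Use of nicotine replacement therapy (patch and lozenge) will mediate the effect of NRTS on biochemically confirmed abstinence at 6 months post enrollment". Section 12.3 tests it with a cross-lagged panel model. Its written equation is "In a CLPM, the mediator and outcome at time t is regressed on arm, the mediator at" the wave before, plus the outcome at the wave before. A significant indirect effect, "based on bootstrapped standard errors", is taken as evidence of mediation. No same-wave path from mediator to outcome is written.

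The timing comes from other sections:
- Section 7.4 describes a starter pack "consisting of a 2-week supply of both nicotine patches (14 mg) and lozenges", and section 7.1 confirms 14 days of each product.
- Section 8.3 sets the first smoking and NRT-use assessment as "Data collection timepoint 3, Day 30 (allowable range 28-44").
- Section 6.2 excludes patients with "Use of tobacco cessation medication in the past week", and section 6.1 requires daily or near-daily smoking.
- Section 4.2 lists NRT use as measured at 1, 3 and 6 months, with no baseline wave. It reduces the measure to one yes/no value for the whole 6 months, plus days of use.
- Section 9.1.4 says that the 1-month survey records both past-7-day use and ever use of patch and lozenge.

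**The concern.** A lagged model can attribute an effect to the mediator only if the mediator is seen to change at an earlier wave than the outcome. In the first interval it cannot. At baseline everyone smokes and recent medication users are excluded, so for NRT use the 1-month abstinence equation reduces to arm plus covariates. A patient who uses the sample in weeks 1-2 and stops smoking by day 28 contributes to arm → 1-month abstinence. The model then carries that gain to month 6 by autoregression, outside the mediator.

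NRT use is the mechanism on which the intervention rests: section 3.1 gives raising it as the goal of sampling. The faster the sample works through that mechanism, the less of the effect the planned analysis credits to it.

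**Working it through.** **1. Written model.** Let A be arm, M NRT use and Y abstinence. With baseline M and Y constant, section 12.3 gives:
- M1 ~ A and Y1 ~ A
- M3 ~ A + M1 + Y1 and Y3 ~ A + M1 + Y1
- Y6 ~ A + M3 + Y3

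Routes through the mediator that remain are A→M1→Y3→Y6, A→M1→M3→Y6 and A→M3→Y6. The absent route is A→M1→Y1→Y3→Y6.

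**2. Anchor.** The protocol states no power for mediation. Table 11.1 (ICC 0.013, 50 × 24, 5.5% vs 10.5%) states 80.3% for the primary outcome. Check: design effect 1 + 23 × 0.013 = 1.299; effective n per arm 600/1.299 = 461.9; SE = √[(0.055 × 0.945 + 0.105 × 0.895)/461.9] = 0.0178; 0.05/0.0178 − 1.96 ≈ 0.85; power 80.3%. All 45 cells reproduce within 0.3 points.

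**3. All quits early, by hand.** Inputs assumed, not in the protocol:
- first-month NRT use 8% ET, 65% NRTS; second-interval use 8% and 15%
- first-month use raises 1-month abstinence by 0.21
- among those not abstinent at the previous wave, 0.02 become abstinent by month 3 and 0.02 by month 6, and second-interval use adds 0.05 to the latter
- abstinence persists with probability 0.6 (month 1 to 3) and 0.7 (month 3 to 6)

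Early route: (0.65 − 0.08) × 0.21 × (0.6 − 0.02) × (0.7 − 0.02 − 0.05 × 0.115) = 0.57 × 0.21 × 0.58 × 0.674 = 0.0468.

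Later-use route: (0.15 − 0.08) × 0.05 × about 0.90 (not abstinent at month 3) = 0.0032.

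The total is 0.0500, all of it truly through NRT use. The planned model labels only the later-use route as indirect: 0.0032/0.0500 = 6%.

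**4. Varying the early share.** Same inputs, total effect 4.7-5.0 points, fully mediated. Shares come from 3 million simulated records. Detection comes from 300 trials of 50 × 24 with 400 practice-bootstrap draws and 95% percentile intervals.

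| Quits by month 1 | Labelled indirect, planned | With M1→Y1 | Detected, planned | With M1→Y1 |
|---|---|---|---|---|
| 100% | 6% | 100% | 7% | 100% |
| 75% | 29% | 100% | 51% | >99% |
| 50% | 53% | 99% | 92% | 100% |
| 25% | 77% | 99% | >99% | 100% |
| 0% | 100% | 100% | 100% | 100% |

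**5. Other inputs.** With first-month use of 70% vs 15% and about 5 points at 6 months, the planned model labels 1% / 24% / 52% as indirect and detects mediation in 6% / 31% / 85% of trials at 100% / 75% / 50% early. That test rejected about 10% of the time under a purely direct effect (150 bootstrap draws), so its detection rates are somewhat inflated. Coding month-3 use as cumulative ever use does not help: 0% / 26% / 52% in a further run with the same use rates.

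**6. Does the added path invent mediation?** Without confounding, no: the mean indirect effect is about 0 when arm acts only directly. With confounding, yes. Assume 30% of patients are motivated, motivation raises both NRT use and quitting, and NRT has no effect. If motivation adds 10 points to 1-month quitting, the added path labels 20% of the effect indirect and is falsely significant in 23% of trials. The planned model gives 5% and 5%. At 20 points the figures are 36% and 38% with the path, against 5% and 6%. In a separate run, false mediation of about 20-25% of a direct effect disappeared once the confounder was adjusted for.

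The runs in steps 4 and 5 assume no confounding, no missing data and linear paths, and step 4 also assumes no practice ICC. The detection rates are therefore optimistic in absolute terms.

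**The case against.** The lag is a deliberate safeguard: it makes the mediator precede the outcome. At month 1, past-7-day use covers the same days as 7-day abstinence, and section 9.1.4 lists no date of first use. A same-wave path would thus take a partly cross-sectional association as causal, and step 6 shows the price. This stands. It is why the lagged model should stay and why the added analysis needs ever use and baseline adjustment.

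Delayed quitting is also foreseen. Section 3.1 expects no immediate quit, section 4.1 allows a quit at any time, and section 7.4 suggests trial use or cutting down and explains how to get more NRT. This stands too. A reader might infer that Hypothesis 3a will be missed, but the documents do not support that: the early share is not stated, and at half early mediation is still detected in 85-92% of simulated trials.

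Two further readings go too far. The model does not test only whether first-month use predicts 3-month abstinence, because the routes through month-3 use remain. Nor do the results carry over to Hypotheses 3b-3d. Those mediators were not simulated, and the intention items in section 4.2 include categories for current use and for having already quit, so a same-wave path would partly put the outcome into the mediator.

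Finally, the path diagram ("Cross lagged panel model for testing mediation. Covariates omitted for clarity") is not reproduced in the text at hand and might show a same-wave path. The written equation has none. A same-wave residual correlation would not help, since a covariance is not part of the indirect effect.

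**Conclusion.** The concern holds in a bounded form. For Hypothesis 3a the written model omits the route from first-month NRT use to 1-month abstinence. The indirect effect is therefore biased towards zero by roughly the share of the effect that arises before the first follow-up. Under the assumed inputs, about half of a fully mediated effect is labelled indirect at 50% early, about a quarter at 75%, and 0-6% at 100%. The hypothesis is likely to be missed only towards the upper end of that range. The direction follows from the protocol's own equation and timing; the size rests on assumed use, persistence and early share. The primary, quit-attempt and smoking-heaviness analyses are unaffected.

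**What to change.** In section 12.3, for Hypothesis 3a only:
- Add a mediation analysis with ever use of patch or lozenge by month 1 as mediator and 6-month CO-verified abstinence as outcome, without conditioning on 1-month abstinence. Alternatively, add the M1→Y1 path and count it in the indirect effect. The first version captures only first-month use: in step 3, 0.0468/0.0500 = 94%, leaving the later-use route to the lagged model.
- Use the ever-use item already in the 1-month survey, with its reference period stated as since enrolment. Past-7-day use at day 28-44 can miss a sample finished by day 14.
- Adjust for baseline interest in quitting, confidence to quit, cigarettes per day and time to first cigarette, all collected under section 9.1.2.
- Report this beside the lagged-only model, and state that a null lagged-only result is not evidence against mediation by NRT use.
- Reconcile the single 6-month yes/no coding in section 4.2, which supplies no wave-by-wave values, with the wave-based model.

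The cost is plan wording and one further analysis. The statistical price is that the added estimate assumes no unmeasured confounding of NRT use and quitting. The M1→Y1 version also assumes that use came before the quit.
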